7.5.5 End-of-Study Visit

If the subject is withdrawn from the study, and thus no subsequent visits are planned, then the Investigator must complete all applicable final visit procedures (e.g., safety laboratory procedures, ECG, physical examination, vital signs) and applicable eCRF pages for subjects who discontinue treatment and include the reason for discontinuation of treatment. If the subject discontinues during the Induction Therapy, the assessment listed in Table 9.1 for Follow-up 3 should be performed at the End-of-Study visit. If the subject discontinues during OLE/LTE Therapy, the assessments listed in Table 9-2 for Follow-up 3 should be performed at the End-of -Study visit.

If the End-of-Study visit is the same as the End-of-Treatment visit then the End-of-Treatment visit assessments should be performed and the End-of-Treatment visit will also be the End-of-Study (end-of-trial) visit.

Once subjects discontinue participation from the study, they will revert to the care of their usual physician for treatment/management of their condition/disease as appropriate.

7.6 Replacement of Subjects

A subject who withdraws after randomization will not be replaced and may not re-enter the study.

8 TREATMENT OF SUBJECTS

8.1 Investigational Product(s)

KHK4083 investigational product, 100 mg/vial (100 mg/mL, 1-mL label fill), is supplied as a single-use, preservative-free solution for IV infusion. The KHK4083 investigational product is a sterile, non-pyrogenic, clear to slightly opalescent, colorless to slightly brownish-yellow solution essentially free of visible particulates. The product is formulated at a concentration of 100 mg/mL in L-histidine, D-sorbitol, L-methionine, Polysorbate 80, and hydrochloric acid, pH 5.5. The 100 mg/vial presentation is contained in 3-mL clear, United States Pharmacopoeia (USP) Type I glass vials that are stoppered with rubber stoppers and sealed with aluminum seals. A volume of 1.3 mL of KHK4083 investigational product is filled per vial. A 0.3-mL over-fill is included in each vial to account for vial, needle, and syringe holdup.

Placebo for KHK4083 is supplied in the same container closure system and contains the same deliverable volume and excipients as KHK4083 investigational product without the active ingredient.

8.1.1 Recommended Storage and Use Conditions

The investigational products (KHK4083 and placebo) should be stored in a secure, limited-access area at a temperature of 2°C to 8°C (36°F to 46°F) and protected from light. The vials should not be shaken.

Guidance on the dilution procedure and recommended storage conditions for diluted solutions of KHK4083 investigational product and placebo can be found in the Pharmacy Manual.

8.1.2 Investigational Product Destruction

Upon completion or termination of the study, all vials (used and unopened) of KHK4083 and placebo must be destroyed upon authorization by the Sponsor and according to the investigative site's biohazardous waste procedures and local regulations.

It will be the Investigator's responsibility to arrange for disposal of all investigational products with containers, provided that procedures for proper disposal have been established according to applicable regulations and institutional guidelines and procedures, and provided that appropriate records of disposal are kept.

[figure not shown]
A copy of the certificate of destruction must be placed in the Sponsor's Trial Master File. Refer to the Pharmacy Manual for additional details on the destruction of investigational product.

8.1.3 Dosage and Administration

8.1.3.1 Selection of Doses

The first human study (Study 4083-001, A Single-Ascending-Dose Phase 1a Study and Placebo-Controlled, Double-blind, Single-Ascending-Dose Phase 1b Study of an Anti-OX40 Monoclonal Antibody [KHK4083] in Subjects with Mild-Moderate Plaque-Type Psoriasis) was conducted in 68 subjects. Dose escalation of KHK4083 was started at 0.003 mg/kg (Cohort 1), followed by single ascending dose cohorts of 0.01, 0.03, 0.1, 0.3, 1.0, and 3.0 mg/kg (Cohorts 2 - 7) administered as 60-minute IV infusions. A single SC dose of 1.0 mg/kg (Cohort 8) also was administered. This study was amended to include an additional single ascending dose cohort of 10 mg/kg (Cohort 9) administered as a 120-minute IV infusion. The doses selected for the current study (4083-002) are based on the Phase 1a/1b study, which showed that KHK4083 was well tolerated and there were no dose-limiting adverse effects at doses \leq 10 mg/kg.

The PK data from IV dose Cohorts 1 to 7 and Cohort 9 were analyzed using a non-linear-mixed-effect modeling technique. Significant departure from dose proportionality was observed as the terminal elimination rate decreased with increasing dose. This is possibly related to target-mediated drug disposition. Simultaneous modeling of all PK data was performed. A two-compartmental PK disposition model described PK profiles well with apparent effect of dose on clearance. Hence, trial simulations were performed for the present Phase 2 multiple ascending dose study of KHK4083 for administration every 2 weeks or every 4 weeks at 1.0, 3.0, and 10 mg/kg as a 60-minute (\pm 10 minutes) IV infusion. Simulated PK profiles are shown in Figure 8.1-1.

Figure 8.1-1 Simulated Pharmacokinetic Profiles Following Multiple-dose Administration of KHK4083 for Study 4083-002

The following PK parameters were estimated based on the simulation outputs: trough simulated concentration at the end of steady-state dosing interval ($C_{\min-ss}$), maximum simulated concentration at steady-state dosing interval $C_{\max-ss}$, area under the curve at steady state during a dosing interval (AUC_{2wk}), accumulation ratio calculated as AUC_{2wk} for the last interval divided by AUC_{2wk} for the first interval (R_{ac}). The results are shown in Table 8.1.3-1.

Table 8.1.3-1 Simulated Pharmacokinetic Parameters for the KHK4083 Once Every 2 Weeks Dosing Regimen

KHK4083 Dose (mg/kg)	AUC_{2wk} ($\mu\text{g}\cdot\text{hr}/\text{mL}$)	R_{ac}	$C_{\min-ss}$ ($\mu\text{g}/\text{mL}$)	$C_{\max-ss}$ ($\mu\text{g}/\text{mL}$)	$t_{1/2}$ (days)
1.0	6230	1.62	10.9	36.9	10.5
3.0	29200	2.17	62.1	140.0	16.3
10	159000	3.14	385.0	645.0	26.2

AUC_{2wk} =area under the concentration-time curve at 2 weeks post-dose; $C_{\max-ss}$ =maximum simulated serum concentration at steady state; $C_{\min-ss}$ =trough simulated concentration at the end of the dosing interval at steady state; R_{ac} =accumulation ratio; $t_{1/2}$ =terminal elimination half-life.

In the 26-week GLP toxicology study in male and female cynomolgus monkeys (SBL303-104) at the NOAEL of 30 mg/kg, the mean AUC_{0-2wk} and C_{\max} were 301500 $\mu\text{g}\cdot\text{hr}/\text{mL}$ and 1510 $\mu\text{g}/\text{mL}$, respectively, after the 13th dose (i.e., steady state). The safety margins (AUC_{0-2wk} from the monkey NOAEL/ AUC_{2wk} simulated in humans) were 48.4, 10.3, and 1.9 at 1.0, 3.0, and 10 mg/kg, respectively (Table 8.1.3-2).

In the 4-week GLP toxicology study in male and female cynomolgus monkeys (SBL303-081) at the NOAEL of 100 mg/kg, the mean $AUC_{0-\infty}$ and C_{\max} were 607000 $\mu\text{g}\cdot\text{hr}/\text{mL}$ and 5345 $\mu\text{g}/\text{mL}$, respectively, after the first dose. The safety margins ($AUC_{0-\infty}$ from the monkey NOAEL/ AUC_{2wk} simulated in humans) were 97.4, 20.8, and 3.8 at 1.0, 3.0, and 10 mg/kg, respectively (Table 8.1.3-2).

Table 8.1.3-2 Safety Margins for the Planned KHK4083 Doses

KHK4083 Dose (mg/kg)	26-week GLP Toxicology Study ^a		4-week GLP Toxicology Study ^b	
	Safety Margin for AUC _{2wk}	Safety Margin for C _{max-ss}	Safety Margin for AUC _{2wk}	Safety Margin for C _{max-ss}
1.0	48.4	40.9	97.4	144.9
3.0	10.3	10.8	20.8	38.2
10	1.9	2.3	3.8	8.3

a: In the 26-week GLP toxicology study in male and female cynomolgus monkeys (SBL303-104), at the NOAEL of 30 mg/kg, the mean AUC_{0-2wks} and C_{max} were 301500 µg·hr/mL and 1510 µg/mL, respectively, after the 13th dose. Safety Margin=AUC_{0-2wk} from monkey NOAEL/AUC_{2wk} simulated in humans. Safety Margin=C_{max} from monkey NOAEL/C_{max} simulated in humans.

b: In the 4-week GLP toxicology study in male and female cynomolgus monkeys (SBL303-081), at the NOAEL of 100 mg/kg, the mean AUC_{0-∞} and C_{max} were 607000 µg·hr/mL and 5345 µg/mL, respectively, after the first dose. Safety Margin=AUC_{0-∞} from monkey NOAEL/AUC_{2wk} simulated in humans; Safety Margin=C_{max} from monkey NOAEL/C_{max-ss} simulated in humans.

AUC_{2wk}=area under the concentration-time curve at 2 weeks post-dose; AUC_{0-∞}= area under the serum drug concentration-time curve from 0 to infinity; C_{max-ss}=maximum observed serum concentration at steady state; GLP=Good Laboratory Practice; NOAEL=no-observed-adverse-effect level.

The safety margins calculated based on C_{max} are comparable to the safety margins calculated based on AUC_{2wk}. As the Phase 2 study is to reach the PK exposure at the NOAEL dose level, and the 1.0, 3.0, and 10 mg/kg doses given every 2 weeks or every 4 weeks are expected to have overall PK exposure lower than the NOAEL, the selected doses are expected to be a safe dose for this clinical study.

8.1.3.2 Administration

Treatment will be administered on an outpatient basis. The minimum IV infusion time will be 60 minutes (± 10 minutes).

8.1.3.3 Infusion Reactions

This study must only be performed in medical facilities with the necessary equipment and medications, and staff trained in their use, readily available to manage potential acute infusion reactions, including anaphylactic reactions.

No pre-medication (e.g., anti-emetic; 5HT3 blocker; histamine H1 and/or H2 blocker(s); corticosteroid) is planned to be routinely/prophylactically administered prior to KHK4083 infusion in this study. However, the administration of therapeutic mAbs, even those that are humanized or fully human, may be associated with acute infusion reactions, especially with the first infusion. Therefore, each subject must be carefully monitored at the investigative site for signs of acute, potential dose-limiting infusion reactions during and for at least 3 hours

following the completion of the first and second IV infusions of investigational product in both phases, and for at least 1 hour following all other IV infusions. In addition, a phone call to each subject will be conducted at approximately 48 to 72 hours following the completion of the first and second infusions for any subject who does not return for a visit at the investigative site.

Acute infusion reactions should not be classified as anaphylaxis unless symptomatic bronchospasm and/or allergy-related edema/angioedema is/are the principal clinical manifestation(s). (Refer to diagnostic criteria for anaphylaxis in Appendix 5). Signs and symptoms of acute infusion reactions usually develop during or shortly after drug infusion and generally resolve completely within 24 hours of completion of the infusion. Acute infusion reactions should be classified by intensity (i.e., mild, moderate, or severe) of the AE. Refer to Section 10.6.7.1 for reporting an infusion reaction including descriptions of specific symptoms observed or reported by the subject.

Although mild infusion reactions require no intervention and no interruption of the infusion, investigators are permitted to interrupt the infusion for mild reactions, observe the subject for resolution of any signs/symptoms, and restart the infusion at one-half the infusion rate originally prescribed if the reaction substantially resolves. The rate of the remaining infusion may be gradually escalated to the originally prescribed rate based on the subject's subsequent tolerance and Investigator judgment. For subjects who continue treatment, subsequent infusion(s) may be recommended to be administered at a slower infusion rate.

If a moderate infusion reaction occurs, stop the infusion for at least 15 to 30 minutes. Paracetamol orally and diphenhydramine 50 mg IV or an equivalent anti-histamine may be administered. If symptoms abate, re-start the infusion at one-half the previous rate; if symptoms recur, permanently discontinue the infusion. For reactions that do not abate after 30 minutes, worsen or recur, the Investigator should use their medical judgment to consider additional medical measures.

For any subject experiencing an acute infusion reaction of severe intensity, the infusion must be immediately discontinued and the subject must receive immediate medical/nursing assessment and indicated supportive management per the institutional standard of care and local Investigator judgment until the signs/symptoms of the reaction have resolved.

If consistent mild and/or moderate infusion reactions are observed, the Sponsor (i.e., Medical Monitor and/or a representative from Drug Safety Surveillance) and the Investigator (or designee) may recommend the pretreatment of subjects or a slower infusion rate. In the event that any subject experiences an acute infusion reaction considered to be an SAE, there

may be a decision to introduce, for all subjects, a slower infusion rate for administration of the investigational product, and/or a mandatory pre-medication regimen (e.g., anti-emetics; H1 or H2 blockers; and/or corticosteroids), and/or dose-reduction in a cohort.

8.1.3.4 Dose Modifications

Management of severe or intolerable adverse reactions due to study treatment may require concurrent therapy, dose omission, prolonged infusion time, or temporary withholding or permanent discontinuation of treatment. No dose reduction should be planned for subsequent doses for an individual subject.

Doses chosen for each cohort, as determined by the Safety Monitoring Committee and Sponsor, may result in dose reduction for all subjects enrolled in a cohort.

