7.5.3 Criteria for Subject Removal from Treatment and the Study

In the absence of a medical contraindication or significant protocol violation, every effort will be made by the Investigator to keep the subject in the study. However, if the Investigator concludes that it is in the best interest of the subject to discontinue administration of the investigational product, including subjects who have not benefited from treatment or should

the subject decide to discontinue study treatment, all efforts will be made to complete and report the observations as thoroughly as possible.

Investigational product administration will be stopped if any of the following events occur:

- Subject experiences a second SUSAR of the same SOC;
- Subject experiences a severe AE that is related to the investigational product;
Investigational product administration may be withheld for up to 2 weeks if the subject experiences a severe event in which it is unclear if the event is related to the investigational product. This will allow the Investigator to determine if the event is related to the investigational product prior to removing the subject permanently from the study.
- Subject experiences a severe, acute infusion reaction despite administration of a prophylactic pre-medication regimen or if the subject experiences anaphylaxis regardless of having received a pre-medication regimen or not. Anaphylaxis has symptomatic bronchospasm and/or allergy-related edema/angioedema as the principal clinical manifestation(s); refer to the clinical diagnostic criteria of anaphylaxis defined in Appendix 5);
- Subject has two consecutive visits during Induction Therapy with a worsening from Baseline in partial Mayo Clinic score of ≥ 3 points (e.g., partial Mayo Clinic score of 3 at baseline, 6 at Week 2, and 6 at Week 4) or two consecutive visits during maintenance therapy with a worsening from Week 12 in partial Mayo Clinic score of ≥ 3 points at a visit and ≥ 5 points at the next visit unless the Investigator, with agreement from the Sponsor, determines that there has not been clinically significant worsening, in which case the subject may continue to receive study medication at that visit (agreement from the Sponsor is to be obtained for each visit);
- Surgery and/or use of prohibited medications are needed to treat the worsening of UC;
- Subject requires a concomitant medication that is prohibited in the study;

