10.6.5.2 Assessment of Intensity

All AEs will be classified either as mild, moderate, or severe in intensity as defined below:

- **Mild** – Event results in mild or transient discomfort, not requiring intervention, or treatment; does not limit or interfere with daily activities (e.g., insomnia, mild headache).
- **Moderate** – Event is sufficiently discomforting so as to limit or interfere with daily activities; may require interventional treatment (e.g., fever requiring antipyretic medication).
- **Severe** – Event results in significant symptoms that prevents normal daily activities; requires interventional treatment and may require hospitalization or invasive intervention (e.g., anemia resulting in blood transfusion).

Refer to Section 7.5.3 regarding withholding investigational product administration if the subject experiences a severe AE not related or of unclear relationship to the investigational product; and discontinuing investigational product administration if the subject experiences a severe AE related to the investigation product.

The Investigator will be instructed to closely monitor each subject who experiences an AE (whether ascribed to the investigational product or not) until the outcome of the AE has been determined. The AE must be monitored until the return to the subject's baseline condition or until clinically satisfactory resolution is achieved (e.g., Grade 1 or stable).

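### A severe, treatment-related adverse event falls under a mandatory stop in Protocol 7.5.3 and an optional menu in 8.1.3.4, and no precedence is stated

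*Protocol*

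**What the plan says.** Protocol 7.5.3 opens its list of criteria with "Investigational product administration will be stopped if any of the following events occur". Three parts of the list matter here:

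- One criterion is "Subject experiences a severe AE that is related to the investigational product". It has no condition on pre-medication and no exception for infusion reactions.
- The text attached to that criterion allows a pause: "Investigational product administration may be withheld for up to 2 weeks if the subject experiences a severe event in which it is unclear" whether the product caused it. The stated purpose is to settle relatedness before the subject is permanently removed.
- A separate criterion is "Subject experiences a severe, acute infusion reaction despite administration of a prophylactic pre-medication regimen". The same bullet stops dosing for anaphylaxis with or without pre-medication.

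Section 10.6.5.2 points back to 7.5.3 and describes the consequence of a severe related event as discontinuation.

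Section 8.1.3.4 says: "Management of severe or intolerable adverse reactions due to study treatment may require concurrent therapy, dose omission, prolonged infusion time, or temporary withholding". Ending treatment for good comes last in that sentence, as one more alternative. The next sentence rules out dose reduction in an individual's later doses, which presupposes that later doses can follow. The section does not mention 7.5.3.

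Section 8.1.3.3 states that no pre-medication "is planned to be routinely/prophylactically administered prior to KHK4083 infusion in this study". For a severe infusion reaction it requires the current infusion to end and the subject to receive supportive care. It says nothing about that subject's next scheduled dose. Section 10.6.5.4 nevertheless refers sites to 8.1.3.3 on whether to continue or discontinue product after an acute infusion reaction.

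**The concern.** A severe adverse reaction due to study treatment and a severe adverse event related to the product are the same event in different words. Under 7.5.3 dosing must end. Under 8.1.3.4 ending it is one choice among several, and the others (omitting a dose, slowing the infusion, withholding for a time) make sense only if dosing resumes. A site that consults 8.1.3.4 alone could re-expose a subject whom 7.5.3 would have taken off treatment.

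Two things are at stake. The first is subject safety, because the rule decides re-exposure after a severe drug-related reaction. The second is how the safety results read. Treatment discontinuation due to adverse events is part of the primary safety endpoint (Protocol 10.1.2; SAP 3.5). If sites resolve the two sections differently, that count partly reflects which section a site consulted.

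**Working it through.** The plan gives no figure on this point and no arithmetic applies. The check is to put each type of event through every section that covers it.

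1. **Severe, related, not an infusion reaction.** 7.5.3: stop. 10.6.5.2: discontinue. 8.1.3.4: omission, temporary withholding or permanent discontinuation are all open. *Result: mandatory against optional.*

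2. **Severe, related infusion reaction, not anaphylaxis, no pre-medication.** 7.5.3 severe-related criterion: stop. 7.5.3 infusion-reaction criterion: not met, because there was no pre-medication. 8.1.3.3: end this infusion, nothing on later doses. 8.1.3.4: the optional list, including a longer infusion. *Result: the conflict in case 1, plus doubt about what the pre-medication condition is for.*

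3. **As case 2, but with pre-medication.** Both 7.5.3 criteria: stop. 8.1.3.4: still the optional list. *Result: the conflict in case 1 only.*

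4. **Anaphylaxis.** 7.5.3: stop, whatever the pre-medication. *Result: the pre-medication ambiguity does not arise.*

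5. **Severe, relatedness unclear.** 7.5.3: hold for up to 2 weeks. 10.6.5.2: consistent. 8.1.3.4 is not engaged until the reaction is attributed to treatment. *Result: no conflict.*

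6. **Severe, not related.** 10.6.5.2 cites 7.5.3 for "withholding investigational product administration if the subject experiences a severe AE not related or of unclear relationship to the investigational product". A later bullet in 7.5.3, on any clinical adverse event, asks the investigator to separate events needing only an interruption from those needing discontinuation. *Result: no conflict, although the provision is general.*

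The conflict is therefore confined to severe events judged related (cases 1 to 3), and the extra ambiguity to case 2. Because 8.1.3.3 plans no routine pre-medication, case 2 is the usual setting for a first severe related infusion reaction, unless pre-medication has since been introduced as 6.3 and 8.1.3.3 allow.

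On the pre-medication condition: if every severe related reaction already stops dosing, the condition makes a difference only for severe infusion reactions judged not related. Section 10.6.7.1 requires that judgement for each reaction, so the condition is not empty. But a reader meeting a criterion limited to reactions despite pre-medication will naturally infer that a reaction without it was meant to be handled otherwise.

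**The case against.** The strongest reply is that the protocol, read as a whole, already has an answer. The 7.5.3 list is specific and mandatory, 10.6.5.2 repeats it and names it as the source, and 6.5.1 tells sites to follow the applicable stopping rules. Section 8.1.3.4 only describes what management may require, it includes permanent discontinuation, and its lesser options have a proper use for reactions that are intolerable but not severe. On that reading a site that re-doses after a severe related event breaches 7.5.3.

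Much of this stands, and it limits the point to mandatory against optional. It does not remove the conflict. Section 8.1.3.4 names severe reactions due to treatment expressly, does not reserve the lesser options for non-severe ones, and does not yield to 7.5.3. No section states which prevails.

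Four stronger readings are tempting but unsupported:

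- *A reader might infer that 7.5.3 expressly contradicts itself.* It does not. Any one criterion is enough, so failing to meet the infusion-reaction criterion gives no permission to continue. The difficulty is one of implied intent.
- *A reader might infer that 10.6.5.2 cites a rule on unrelated events that 7.5.3 lacks.* The general bullet on interruption against discontinuation supplies one.
- *A reader might infer that every first severe infusion reaction is caught.* Anaphylaxis stops dosing regardless, reactions judged unrelated do not meet the severe-related criterion, and pre-medication may have been introduced by then.
- *A reader might note that one of 9 active subjects in a Part A cohort is 1/9 = 11.1 percentage points and infer that such a shift drives dose escalation.* The documents set no discontinuation-rate threshold. The Safety Monitoring Committee reviews cumulative safety data at a point defined by the first 8 randomized subjects (6.3), and the termination examples in 7.5.2 concern infections and unexpected serious reactions. The committee's detailed procedures are in a separate charter.

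**Conclusion.** The point holds as an internal inconsistency. For a severe adverse event related to the product, one section requires stopping and another offers stopping as one option, with no cross-reference or order of precedence. For a severe, related, non-anaphylactic infusion reaction without pre-medication, the stopping criterion is further blurred by the wording of the infusion-reaction criterion and by a referral to a section that does not address later doses.

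Its reach is every severe related event in any cohort and treatment phase. How many that would be is unknown, because the documents give no expected rate, and no effect on dose escalation can be shown from them. The conclusion assumes that an adverse reaction due to study treatment means a related adverse event, and that no document outside the protocol and SAP settles precedence. Even with few events the inconsistency should be removed, because it bears on re-exposure and on a component of the primary safety endpoint.

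**What to change.** Reconcile Protocol 7.5.3, 8.1.3.3, 8.1.3.4, 10.6.5.2 and 10.6.5.4. State a single outcome for each of:

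- a severe related event that is not an infusion reaction;
- a severe, related, non-anaphylactic infusion reaction without pre-medication;
- the same reaction with pre-medication.

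Say which section takes precedence, put a cross-reference to it in 8.1.3.4, and have 8.1.3.3 either address later doses after a severe infusion reaction or point to the section that does. Which outcome applies in each case is for the sponsor's physicians; this review takes no position.

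The cost is wording in an amendment and a clarification memo to sites, with no added procedures or visits. The drawback is less discretion for investigators.
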